Studies on performance measures: *Prospective studies:* The STORM-trial in Italy (8), the Oslo trial in Norway (7), and the Malmo-trial from Sweden (9) compared performance measures (i.e. recall rate, cancer detection, positive predictive value, tumor characteristics) within women screened with DM and DBT with DM or 2D. The STORM trial compared the outcome of sequential screen-readings; the same radiologists read DM first, and thereafter DBT. A significant higher rate of screen-detected cancer, 2.7/1000 and a lower recall rate was found for DM+DBT compared with DM. The Oslo trial assigned the radiologists to read DM or DM+DBT. They found an increase of 1.9 cancers/1000 screens using DM or 2D+DBT. The additional cancers were mostly invasive cancers. The recall rate decreased. The Malmo-trial compared the outcome of two-view DM with one view DBT. A significant increase of 2.6 cancers/1000 screened for one-view DBT was observed. The recall rate increased. The majority (17 of 21) of the cancers were invasive. *Retrospective studies:* Results from eight retrospective studies of DBT adjunct to DM are available of today (10-17). All the studies are conducted in the U.S. where the screening protocol differ substantially from the one used in Norway and Europe (18). Two of the studies (12, 13) compared performance measures before and after the introduction of DBT, while Haas et al. (10) compared the outcome of DM versus DM+DBT within the same timeframe. A clear trend toward a higher rate of screen-detected cancer and a reduction in recall rate were observed in all the studies.

Economic studies: Only two studies, both from the U.S. have considered the costs of DBT (27, 28). One of the studies concluded that DM+DBT resulted in cost savings compared with standard DM in a simulated screening cohort, mainly due to fewer recalls and earlier diagnosis, while the other study found that DM+DBT might be cost-effective for women with dense breasts.

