We want to take advantage of the new mammographic equipment (Seno Claire GE Breast Tomosynthesis) installed at the screening unit at Danmarkspllass in Bergen, December 2014, and perform a randomized trial assessing 2D + DBT in two projections (hereafter referred as tomo) versus standard two projections DM as screening tools. The equipment is accepted for screening both in the US and Europe, but no results from studies on human beings are reported in articles of today (34, 35). Measuring the effect of tomo with GE versus standard DM can be done by comparing results of early performance measures and economic aspects in two comparable populations at the same age and residing in the same county, examined by the same radiographers, screen-read by the same radiologists and histologically breast cancer proven by the same pathologists, treated by the same surgeons and oncologists.

The project has a practical and an academic part: 1) The practical part is critical and consists of a four months pilot and 24 months (one screening round) of running the trial. The pilot is aimed at testing feasibility including the time aspect, get experiences and learn how to read tomo, develop a practical hanging protocol and a form to report information needed to assess the research questions right after the screening is performed and eventual diagnosis is stated. The trial will be run as a part of the screening program. Only small changes from the usual setting is acceptable. 2) The academic part aims at investigating early performance measures and economic aspects performed in the practical part. We aim to address the following topics and research questions in the academic part:

Study I: *Early performance measures in a population based screening program using tomo versus DM – interim analyses.* We will compare results of early performance measures.

How do the recall rates, including false positive screening results differ between the two groups? What time is spent in examination and reading with the two technologies? How do the radiation doses differ between the two groups? Due to the small number of women screened and diagnosed with breast cancer during the first year (Table 1), this study will focus on early performance measures related to the time used, recalls and radiation dose. We will compare the outcome for tomo versus DM and according to recommended levels given in the quality assurance manual (36) using standard statistical tests (37).

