How do the early performance measures given in study II+III differ by mammographic density? Volpara® is installed at the screening units at Danmarksplass and data is available for this study. We will use descriptive analyses to compare distributions and rates, while logistic regression analyses will be performed to estimate the odds ratio of recalls and breast cancer (37).

Studies V and VI: Costs of tomo and DM in a population based screening program – Is tomo cost-effective? Study V will deal with early costs related to time spent at screening and reading, the recall rates, diagnostic procedures, treatment and total costs for the two techniques. Data from the first year of the trial will be used. A previous study from Norway, which showed that treatment costs are highest during the first year following a diagnosis will serve as a methodological basis for the analysis (38). Using a similar approach, we will compare treatment costs for interval cancers, recurrence and early costs of cancers detected in the following screening round, using the full two year follow-up in Study VI. Results will be presented as cost per recurrence, interval and subsequent breast cancer avoided. Possible differences between groups in these outcomes should be well captured during the two years. Mortality may also be used as an additional outcome in the cost-effectiveness analysis in If the project is sufficient funded, study VI, although the follow-up time is too short, will use a simulation model with mortality estimates from the Cancer Registry. Additional cost estimates for the period beyond two years will be run (33) as inputs can be run to estimate the cost-effectiveness in the life-long perspective for the women (as e.g. in (28)). A major advantage of Studies V and VI compared with the U.S. studies (24, 25), is the availability of individual level data within the project, thus avoiding most assumptions of recall rates, cancer stage distributions, diagnostic and treatment costs etc. from earlier studies. This ensures a higher level of detail when defining the list of cost components, and more precise estimates of the variation across patients in both effect outcomes and costs.

A prospective cohort study: We will perform a prospective cohort study. During the study period, about 45,000 women will be invited to screening at Danmarksplass and 35,000 (75%) are expected to participate (Table 1).

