This project is aimed at performing a randomized trial investigating the effect of early performance measures and economic aspects of tomo versus DM in a screened population. All studies will be performed with data from women screened at Danmarkspllass. The pilot will be performed Aug-Dec 2015, while the trial period is set to Jan 2016-Dec 2017 (Table 2). Complete data for analyses of early performance measures related to the screening exam will be available after the end of the trial. However, we will follow the women for information about treatment and therapy, interval and breast cancer in the next screening round, recurrence and metastasis, two years after screening exam. These follow-up results are of utmost interest for the complete effect of tomo versus DM in a clinical and economic perspective.

Data collection: All studies will be based on the same dataset, except for # I and V, which are based on data collected from the first year of the trial.

Clinical data: Data related to screening participation will be extracted from the Norwegian Breast Cancer Screening Program's Database, located at the Cancer Registry of Norway. Technical data regarding mammographic density and radiation doses is considered part of the screening data. Data related to needle biopsies and treatment will be collected immediately after the diagnosis, particularly for this study, for the study period (2016-17) and the follow-up time (2018-19). These data is needed immediately to keep the study results updated and to keep the time schedule. A close collaboration with the pathologists and surgeons at Haukeland University Hospital ([name] and [name])

is already established. Research assistants will be responsible for collecting, reporting, and coding the trial and follow-up data.

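### Study V puts cancer treatment into a first-year total cost per technique with no common horizon, which tilts the total against tomo to the extent that extra cancers are brought forward

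*Combined protocol and SAP*

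**What the plan says.** Section 2, under Studies V and VI, sets out the first cost paper. It covers the early costs of examination and reading time, together with "the recall rates, diagnostic procedures, treatment and total costs for the two techniques". It then fixes the window: "Data from the first year of the trial will be used". The Data collection paragraph in section 3 repeats the limit: all studies share one dataset "except for # I and V, which are based on data collected from the first year of the trial".

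The method for Study V rests on an earlier Norwegian finding that "treatment costs are highest during the first year following a diagnosis". Study VI, with two years of follow-up, will "compare treatment costs for interval cancers, recurrence and early costs of cancers detected in the following screening round". It will express results as cost per recurrence, interval cancer and subsequent cancer avoided. The two studies share one heading, which asks whether tomo is cost-effective.

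The practical part of the project includes "24 months (one screening round) of running the trial". In Table 2, paper V is scheduled for January to September 2018. Paper VI is scheduled for October 2018 to March 2019 and carries the qualifier Evt, read here as 'possibly'. Analysis of interval and subsequent cancers comes in 2020, on the group's own budget.

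**The concern.** Treatment is a legitimate cost, but a comparison of treatment totals is fair only if both arms are followed long enough for the same cancers to appear in each. The background reports higher detection with tomosynthesis in all three prospective trials. For the Malmö trial, for example: "A significant increase of 2.6 cancers/1000 screened for one-view DBT was observed". If such a gain occurs here, treatment of the extra cancers enters the tomo total at once. Cancers that DM missed but that would still surface later do so as interval or next-round cancers, mostly after Study V's window has closed. The plan sets no equal horizon for Study V, does not adjust for lead time, and does not confine the between-arm comparison to costs unaffected by it.

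At stake is how the first cost paper is read. Its total would mix what tomo screening costs with when cancers happen to be treated, and it would appear before Study VI under a heading about cost-effectiveness.

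The plan's own reasoning points the same way. Study I is confined to time, recalls and dose because few cancers are diagnosed in the first year. Study V uses data from the same year but adds cancer treatment.

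**Working it through.** The documents give no computed figure for Study V. Their one design figure is a detectable difference of 0.25 percentage points (section 2, Power estimations). It reproduces on the detection rate. With 17,500 per arm and 6.0 against 8.5 per 1000, two-sided 5% (sidedness assumed), power is 0.787, and the detectable difference at 80% power is 0.2545 points. On the 3% recall rate, power for the same difference is only 0.27 to 0.29. The inputs below are therefore the plan's own.

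**Inputs**
- 17,500 women per arm (Table 1 and Budget). The whole study has about twice the women of Study I, so year 1 has 17,500 / 2 = 8,750 per arm.
- Screen-detected cancers 6.0 per 1000; interval cancers 2.0 per 1000 (Table 1).
- Detection gain with tomosynthesis 1.9 to 2.7 per 1000 (section 2, prospective studies).
- Equal treatment cost per cancer. This is an assumption, because the documents give no unit cost.

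**Step 1: trial-screen cancers in year 1**
- DM: 8,750 × 0.0060 = 52.5.
- Extra on tomo: 8,750 × 0.0019 = 16.6 to 8,750 × 0.0027 = 23.6, an increase of 32% to 45%.
- At Table 1's equal rates: 0 extra.

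**Step 2: interval cancers inside the window**
- Over 24 months: 8,750 × 0.0020 = 17.5 per arm.
- Calendar year 1, with uniform screening and a constant rate (assumed): mean follow-up is 0.5 of 2 years, so 25%, or 4.4.
- Twelve months per woman, same constant rate: 50%, or 8.75.
- Next-round cancers: none, because the round is 24 months.

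**Step 3: net excess of treated cancers on tomo in the window**

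The smallest excess arises if every extra cancer would have been an interval cancer under DM. That is possible only at the 1.9 gain, since DM has just 2.0 interval cancers per 1000. The largest arises if none would have been.
- Calendar year 1: 16.6 × (1 − 0.25) = 12.5, up to 23.6. On a DM base of 52.5 + 4.4 = 56.9, the ratio is 1.22 to 1.42.
- Twelve months per woman: 16.6 × (1 − 0.50) = 8.3, up to 23.6. On a DM base of 52.5 + 8.75 = 61.25, the ratio is 1.14 to 1.39.

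**Step 4: how much of this is timing**

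Timing tilt = excess in the window − excess once 24 months and the next round are included.
- All extra cancers brought forward: the long-horizon excess is 0, so the whole window excess (8.3 to 23.6) is tilt.
- Half over-diagnosed, the other half otherwise found at the next round (assumed): the long-horizon excess is 8.3 to 11.8, so the tilt is 16.6 − 8.3 = 8.3 to 23.6 − 11.8 = 11.8.
- All over-diagnosed: the tilt is 0.

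**Step 5: chance**

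Even with equal detection, the difference between two Poisson counts of 52.5 has SD √105 = 10.2. The 95% range is about ±20 cancers, or ±2.3 per 1000. A first-year treatment total is thus as exposed to chance as to the tilt.

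**The case against.** The strongest reply is that the plan already handles this. Study V is described as early costs and lists treatment as an item beside the total. Later costs go to Study VI with two years of follow-up, and the heading about cost-effectiveness covers both studies. A short-horizon total, clearly labelled, is a fair description of early spending. Taking treatment out altogether would hide the cost of treating over-diagnosed cancers, which the plan names as a concern. These points stand, and they are why treatment should remain visible as its own line.

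They do not remove the problem. A total per technique is still promised from first-year data, and the plan nowhere calls it short-horizon. Study VI's listed treatment costs do not name trial-screen cancers, and Table 2 makes paper VI conditional.

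Four stronger readings are tempting, but the documents do not support them.
- A reader might infer that tomo would look dearer by timing alone. The timing share can lie anywhere from 0% to 100%, and tomo also has real reading and equipment costs.
- A reader might infer that the plan assumes a detection gain. Table 1 has 105 screen-detected cancers in each arm, and the text says only that detection may rise, on evidence from two other vendors.
- A reader might infer that the two studies' costs will never be combined. The plan is silent; Study VI uses the full dataset, and a cost per cancer avoided would normally need an incremental cost that includes the trial screen.
- A reader might set treatment against the budget line for extra reading and forms, 623K NOK / 17,500 = 36 NOK per exam. That line leaves out storage, investment and recorded examination time, and any treatment cost per cancer would be assumed. No monetary tilt can be computed.

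The window is also ambiguous. It may mean women screened in year 1 with later follow-up. That narrows the gap, but next-round cancers would still mostly fall outside.

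**Conclusion.** The point holds conditionally. Study V, as written, yields a first-year total per technique that includes treatment without a horizon long enough to balance the arms. If tomo detects 1.9 to 2.7 more cancers per 1000, the tomo total carries about 17 to 24 extra treated cancers on a DM base of 52.5. Net of interval cancers this is 12.5 to 23.6 in calendar year 1, or 8.3 to 23.6 with 12 months per woman. The part brought forward is a tilt against tomo; the over-diagnosed part is a real cost. With equal detection there is no expected tilt.

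The size rests on half the women being screened in year 1, a constant interval-cancer rate, equal cost per cancer, and detection gains taken from other vendors' equipment. The sponsor should change the plan, because the correction is cheap and paper V is due before Study VI.

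**What to change.** **Study V.** Make screening, reading, recall and diagnostic work-up the main between-arm cost comparison. Show treatment cost as a separate descriptive line, per cancer and per 1000 screened, labelled as partly brought forward and partly possible over-diagnosis. Label any first-year sum as short-horizon and draw no cost-effectiveness conclusion from it. State whether the first year means calendar time or women screened in that year.

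**Study VI.** Report one per-arm total per randomised woman over a common horizon that includes trial-screen, interval and next-round cancers. Use the difference in that total as the numerator for cost per cancer avoided.

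**Cost.** The change needs some wording and one table line. No new data are needed, since treatment data are already to be collected for 2016-17 and for follow-up in 2018-19. The downside is that Study V gives no headline total per technique and the conclusion on total cost waits for Study VI. Paper VI's date also needs a check: women screened after March 2017 will not have two years of follow-up by March 2019, so the paper must move or define a cohort with complete follow-up.

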Sept 2015-Des 2018	Hiring research assistants – responsible for the practical part of the study, collecting, reporting and coding the histopathologic data
Jan 2016-Dec 2017	Running the trial
Jan 2017-Dec 2019	Hiring a PhD student
Jan-Dec 2017	Application for PhD + reviewing the literature Analysis and writing paper I – submission to a peer-reviewed journal
July-December 2017	Preparing programming code for cost data and analysis based on preliminary data
Jan 2018-Sept 2018	Analysis and writing paper II+V – submission to a peer-reviewed journal
Aug 2018-Dec 2018	Analysis and writing paper III – submission to a peer-reviewed journal
Oct 2018-Mar 2019	Analysis and writing paper IV – submission to a peer-reviewed journal
Oct 2018-Mar 2019	Evt Cost analysis – finalizing and submitting papers VI
Feb 2019-May 2019	PhD student: Working with the thesis – finalizing
May 2019-Dec 2019	Finalizing the papers, the project, and prepare for disputation
Dec 2019	Disputation
Jan 2020-Dec 2020	Finalizing the study: Analysing rates, histopathologic characteristics and mammographic features of interval and subsequent breast cancer – on own budget

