
4. Key perspectives and compliance with strategic documents

Mammography is the preferable technology for breast cancer screening and diagnostic today. DBT is assumed to be the next generation screening technology for breast cancer (39). As of today, there is not sufficient evidence about the effect of tomo to implement the technology. This study has a unique possibility to contribute in filling the gap of knowledge needed to assess the technology's potential as a screening tool. If tomo turn out to be a better screening tool compared with DM, the benefits of participating in screening might be improved, whilst the harms will assumingly decline, which is beneficial both for the women screened negative and those diagnosed with breast cancer, both in Norway and in other countries.

Interim analyses will be performed after one year of performance of the study, while the final results will be available 3-6 months after the trial is finished. This is unique in a screening setting. In addition, we will follow the women for interval and subsequent cancer 2 years after the trial is finished. Results from the applied trial and the follow-up represent a unique possibility to analyse data from a substantial number of screened women which no other screening programs are able to do, due to the link between the clinical data, the screening database and data from the incidence database at the Cancer Registry. Norway is in a unique situation with the 11-digit PIN number, the

nationwide screening program and the Cancer Registry, which makes it possible to identify the cancer cases, even if women move from one county to another. These facts make this study unique from an international perspective.

The trial might be able to serve as an example for other screening and diagnostic tests, not only breast cancer and mammographic screening. Implementing new technology should be based on sufficient evidence. This protocol has the possibility to serve as a guide for testing screening and diagnostic tools for other diseases.

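### Table 2 has the Study VI cost paper submitted 9 to 15 months before the two-year follow-up that defines it is complete, and no data cut is stated

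*Combined protocol and SAP*

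**What the plan says.** **Definition of Study VI.** Section 2 (Studies V and VI) sets out the cost comparison for Study VI. It covers the treatment of recurrences and of interval cancers, and it also takes in "early costs of cancers detected in the following screening round, using the full two year follow-up in Study VI". Results are to be expressed as cost per such event avoided. The same paragraph expects two years to capture any differences between the groups well.

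**Follow-up.** Section 3 puts the trial period at January 2016 to December 2017 and follows women for "interval and breast cancer in the next screening round, recurrence and metastasis, two years after screening exam". Under Clinical data, needle-biopsy and treatment data are to be collected "for the study period (2016-17) and the follow-up time (2018-19"). Section 4 words it differently: "we will follow the women for interval and subsequent cancer 2 years after the trial is finished". Section 2 (Approaches, hypotheses and choice of methods) equates one screening round with 24 months.

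**Schedule.** Table 2, October 2018 to March 2019, reads "Evt Cost analysis – finalizing and submitting papers VI". Its last row, January to December 2020, covers "Analysing rates, histopathologic characteristics and mammographic features of interval and subsequent breast cancer" and mentions no cost analysis.

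**Dataset.** Section 3 (Data collection) puts all studies on one dataset and limits only Studies I and V to first-year data. No cut-off date or restricted cohort is given for Study VI.

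**The concern.** Study VI cannot be delivered as defined on the date Table 2 gives it. Its effect measures count recurrences, interval cancers and cancers of the next round. The last of these arise only once a woman returns after about 24 months. If the paper is submitted by March 2019, many women have not reached that point, and some of the interval-cancer period has not been observed either. Costs of the same later cancers would also be incomplete. Table 2 then analyses interval and subsequent cancers after the paper that uses them as its outcome has been sent off.

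At stake are the completeness and precision of one economic paper, and a reader's ability to tell which women and what follow-up it describes. The protocol itself regards the follow-up results as highly important clinically and economically.

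**Working it through.** **1. Reproduce the plan's follow-up period.** First women: January 2016 + 24 months = January 2018. Last women: December 2017 + 24 months = December 2019. This matches the stated follow-up time of 2018-19. The Section 4 wording (two years from the end of the trial) also ends in December 2019.

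**2. Gap to the Study VI window.** Count months from the start of January 2016.
- Accrual runs from month 0 to month 24, and follow-up is complete for all at month 48.
- Window opens at the start of October 2018, month 33: 48 − 33 = 15 months short.
- Window closes at the end of March 2019, month 39: 48 − 39 = 9 months short.

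This step needs no accrual assumption. The last women screened would have 33 − 24 = 9 to 39 − 24 = 15 months of follow-up.

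**3. Women who have reached the next-round date.** Assumptions: even accrual over 24 months, re-examination at 24 months, no reporting lag. For a cut at month c, the share is (c − 24)/24.
- c = 33: 9/24 = 37.5%.
- c = 39: 15/24 = 62.5%.

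These are upper limits, since late attendance, work-up and reporting take further time.

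**4. Interval cancers seen.** Table 1 expects 2.0 per 1,000, and 0.002 × 17,500 = 35 per arm, as stated there. Take the 35 as arising over two years at a constant rate (an assumption). The share seen is the average of min(24, c − m)/24 over screening month m from 0 to 24.
- c = 33: (9 × 24 + 15 × 16.5)/576 = 463.5/576 = 80.5%, or 28.2 of 35.
- c = 39: (15 × 24 + 9 × 19.5)/576 = 535.5/576 = 93.0%, or 32.5 of 35.

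If instead two thirds arise in the second year (also an assumption), the shares are 74.5% and 90.6%, or 26.1 and 31.7 of 35. Either way the loss is much smaller than for next-round cancers.

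**5. Price of restricting by screening date.** Standard errors grow by 1/√(share kept).
- Women screened in 2016: 12/24 = 50%, or 8,750 per arm; 1/√0.50 = 1.41. All have two years by December 2018, and at least 39 − 12 − 24 = 3 further months by the end of March 2019.
- All women with two years elapsed at the end of March 2019: 62.5%, or about 10,940 per arm; 1/√0.625 = 1.26.

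**6. The two follow-up wordings.** A woman screened in January 2016 is followed to January 2018 under Section 3 and to December 2019 under Section 4, almost two years longer. A woman screened in December 2017 is followed to December 2019 under both. She reaches her next-round date just as follow-up closes, with almost no time for next-round events or their costs.

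**The case against.** The best defence is that this is one date in a grant-style schedule. The Table 2 row carries the prefix Evt, which reads as optional. Cost work is visibly staged, beginning on preliminary data in 2017. A later row (May to December 2019) finalises the papers, and 2020 is reserved for interval and subsequent cancers at own cost. Study V uses first-year data, so Study VI might have been meant for women screened in 2016, whose two years end inside the window. Finally, both arms are randomised over the same period, so a common cut is balanced, and most interval cancers would be seen.

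The balance between arms and the modest loss of interval cancers stand. The rest does not remove the conflict. An optional paper still conflicts with its definition if it is run as scheduled. The 2019 row does not name paper VI, whose own row already includes submission, and it ends no later than follow-up does. The 2020 row omits costs. A cohort screened in 2016 would be workable but is nowhere stated, and Section 3 limits only Studies I and V to first-year data. The simulation model in Section 2 depends on funding and serves mortality and the period beyond two years.

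A reader might infer more than the documents support:
- **That the cost-effectiveness result would be biased in a known direction.** Events and costs are both cut short, equally by arm, so neither direction nor size can be stated.
- **That cost collection must run beyond 2019 to give each next-round cancer a year of costs.** The protocol speaks only of early costs, with no length. Its reference to the first year after diagnosis describes an earlier study's finding, not a window for this one.
- **That Sections 3 and 4 contradict each other on when follow-up ends.** They share the end date and differ in length for women screened early.
- **That Study IV, with the same slot in Table 2, fails too because it asks about sensitivity.** Section 2 limits it to the measures of Studies II and III.

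**Conclusion.** The point holds as a conflict between the definition of Study VI and its date in Table 2, together with a missing data cut. The 9 to 15 month gap follows from the protocol's dates alone. The sizes of 37.5% to 62.5% of women at the next-round date, and about 80% to 93% of interval cancers (28 to 33 of 35 per arm), rest on even accrual, re-examination at 24 months, a constant interval-cancer rate and no reporting lag. Next-round cancers are the main loss. The expectation that two years will capture group differences well would not be met for them on the scheduled date.

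The reach is limited to Study VI. Studies I to III and V are unaffected, and so is Study IV if it keeps to the measures stated for it. Weight: minor to should-fix.

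**What to change.** Choose one of two routes and write it into Section 2 and Table 2.

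1. **Wait.** Move the final Study VI analysis to after December 2019 and add it to the January to December 2020 row. Cost: this runs past the 25% economics position budgeted for 2017-19, and the budget already leaves follow-up analyses to own funds.
2. **Keep the date.** State the data cut and restrict both arms, by screening date, to women whose two years have elapsed at that cut. Women screened in 2016 are the natural choice: about 50%, standard errors about 1.41 times larger. At the end of March 2019 at most 62.5% qualify, about 1.26 times. Restrict by date, not by whether follow-up was observed to be complete, so that selection does not depend on what happened after randomisation.

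Under either route, reconcile the follow-up wording of Sections 3 and 4 into one definition, and say how next-round cancers and their costs are counted for women screened late in 2017. Randomisation, screening and the other studies need no change.
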